96 patients per cancer group (48 controls and 48 nutrition therapy), supplemented with 20% per group to take dropouts into account.

Inclusion criteria

- > 18 years
- Male and female
- CRC or NSCLC before chemo- or radiotherapy is started (naive to treatment), but surgery may already have been performed
- CRC or NSCLC relapse > 3 months after initial oncologic therapy
- Oncologic cachexia (undesired weight loss > 5% in less than 6 months)
- Written informed consent / ability to give informed consent

Exclusion criteria

- concomitant second malignancy
- uncertainty of diagnosis of CRC or NSCLC
- patient unfit for chemotherapy
- patient unfit for radiotherapy
- patient unfit for surgery
- palliative treatment or terminal patient (life expectancy < 3 months)
- patient already participating in another study
- Pregnancy / lactation
- Any other pathology present that causes the patient to be unfit for oncologic therapy (e.g. end-stage renal failure, severe COLD, severe heart failure)
- Unable to adhere to protocol instructions (e.g. language barrier)
- Investigator's uncertainty about the willingness or ability of the patient to comply with the protocol requirements
- Participation in any other studies involving investigational or marketed products concomitantly or within two weeks prior to entry into the study

Replacement of subjects

In case of dropout, subjects will be censored on the Kaplan-Meier curves.

[figure not shown]
Restrictions and prohibitions for the subjects

None.

Procedures

See below, to be performed at the oncology consultation.

Flowchart

systematic overview of the study: planned tests per visit of the subjects

Expected total duration of the trial: 2 year (inclusion).

Supervising MD during the tests: Principal Investigator: [name] or co-investigator: [name].

Randomisation/blinding

Computerized randomization, validated for clinical trials, are used.

Prior and concomitant therapy

See "Inclusion and Exclusion criteria". All other concomitant therapy is allowed.

Study analysis

Sample size calculation

The statistical power was calculated based on the pilot trial.

Analysis of the samples

Outcome parameters:

• Body weight
• BIA Bio-Electrical Impedance Analysis
• Blood Pressure
• Blood Sample Analysis
• Caloric and Nitrogen intake
• Indirect Calorimetry
• Sensewear ®
• Body weight
• BIA Bio-Electrical Impedance Analysis
• Blood Pressure
• Blood Sample Analysis
• Indirect Calorimetry
• Body weight, mortality, morbidity.

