- Primary: weight stabilisation, morbidity and mortality
- Secondary: Quality of Life (QoL 36)

Statistical analysis

2-tailed, paired t-tests will be used for statistical analysis.

Quality control and quality assurance

The quality control is performed by the certified and experienced research unit of the Intensive Care Department.

Publication policy

All rights belong to the PI and thus to the VUB/the UZ Brussel.

Protocol Amendment dd 12/06/2017

Background:

Due to lack of patients with 5% weight loss in 6 months and, by consequence, very low inclusion rate, it was decided to amend the protocol. To achieve this, a special cooperation with the department of Radiotherapy was established. The service sees many patients who lose weight during radiotherapy, partly because of cancer-related cachexia, but mostly due to the mucositis caused by radiotherapy itself, losing > 10% of their initial body weight (at the start of their therapy). This is especially seen in cancers of head and neck, oesophagus and stomach. Radiotherapy is performed on working days and treatments typically last 5-7 weeks (depending on indication).

Amendment:

- Inclusion of patients with colorectal, lung and pancreatic cancer will be changed to: Inclusion of patients with lung, gastric, oesophageal, head and neck and pancreatic cancer
- 5% weight loss over the past 6 months will be changed to: patients with the aforementioned cancers where radiotherapy will be part of their treatment (or will be the entire treatment)
- Duration of intervention of 3 months will be changed to: duration of intervention for the entire period of radiotherapy
- After recalculation of statistical power, only 48 patients will be needed instead of 96. With correction for dropouts, this will become 60 patients instead of 120. This means 30 controls and 30 patients in the intervention group.
- The amendment will be added to the registration at *clinicaltrials.gov*.

The procedure and flowchart will remain unchanged. Analysis of the data will remain: in whole, per cancer and per sex (the latter two criteria requiring 60 patients in each group).

Protocol Amendment dd 19/09/2017

Background:

The study has seen much more inclusions and is running well thanks to the previous amendment. Due to a typo, the colorectal cancer group was unfortunately omitted. Also, the absolute difference of survival in the TiCaCo trial after one year was similar to that after the second year.

Amendment:

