- Colorectal cancer patients are still to be included. Otherwise, nothing changes concerning inclusion criteria.
- The follow-up will be shortened from 2 years to one year.
- The amendment will be added to the registration at *clinicaltrials.gov*.

Protocol Amendment dd 05/02/2019

Background:

The study needs 48 inclusions that remain in the study until the end. However, the number of dropouts is too high, severely compromising the study's statistical power. Therefore, an inclusion surplus of 20 - 25% is required.

Amendment:

- The inclusion period will be expanded to 31/12/2019 or the inclusion of 60 patients (including dropouts), whichever is sooner.
- The amendment will be added to the registration at *clinicaltrials.gov*.

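### Dropouts are censored on the survival curves of a primary mortality outcome, with no distinction between leaving the programme and losing vital status, so censoring may be informative

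*Protocol*

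**What the plan says.** The only rule in the protocol on dropouts in the survival analysis stands under Replacement of subjects: "In case of dropout, subjects will be censored on the Kaplan-Meier curves". The outcome list reads "Primary: weight stabilisation, morbidity and mortality", so the rule acts on a primary outcome.

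Dropout is not defined. The text does not say whether vital status is still collected after a patient stops the nutrition regimen or the visits.

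The amendment of 05/02/2019 reports: "However, the number of dropouts is too high, severely compromising the study's statistical power". It gives no rate, no reasons and no split by arm. Its preceding sentence is about numbers: "The study needs 48 inclusions that remain in the study until the end". Follow-up is one year per patient since the amendment of 19/09/2017 ("The follow-up will be shortened from 2 years to one year").

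**The concern.** A Kaplan-Meier curve treats a censored patient as having the same future risk of death as those still under observation. If leaving the programme is linked to prognosis, that fails and the curve is wrong. If the link or the amount of dropout also differs by arm, the comparison is wrong too.

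The protocol gives grounds for doubt:
- The subjects section specifies stage III-IV disease for the two tumour types first planned. The 2017 amendment brings in radiotherapy patients who are expected to lose considerable weight.
- The design line says double-blind, but the objective says that blinding is not possible and the text on both groups calls the trial open label. The strategy being validated adds intensive coaching in one arm. Patients and staff know the arm, and the burden differs.
- Dropout is reported as excessive although an allowance had already been made.

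The result carries weight. The objective has the trial stopped early if survival is significant, and a positive result is meant to make nutrition therapy standard treatment. Death, unlike weight or quality of life, can usually be established without the patient attending. Censoring at dropout therefore gives up information that may be easy to recover.

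**Working it through.** **1. The plan's own dropout arithmetic.** Formula: number to recruit = number needed / (1 − dropout).
- Before amendment: "96 patients per cancer group (48 controls and 48 nutrition therapy), supplemented with 20% per group to take dropouts into account". 96 / (1 − 0.20) = 120 per cancer group, as stated.
- After amendment: "With correction for dropouts, this will become 60 patients instead of 120". 48 / (1 − 0.20) = 60, as stated; 60 / 2 = 30 per arm ("This means 30 controls and 30 patients in the intervention group").
- The 2019 surplus of 20 to 25% fits the same total at its upper end: 48 × 1.25 = 60.

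The allowance reproduces. The base sizes 48 and 96 cannot be checked, because no alpha, power, effect size or event rate is given. Nothing below changes a sample-size figure.

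**2. Bias of a single curve.** All inputs are assumed: 20% dropout within the year, 30% of patients at high risk with 5 times the hazard, true one-year survival about 50%.

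| Who drops out | True | Kaplan-Meier, dropouts censored |
|---|---|---|
| Unrelated to risk | 0.501 | 0.501 |
| High-risk 4 times as fast | 0.501 | 0.528 |
| Low-risk 4 times as fast | 0.499 | 0.486 |

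With 3 to 5 times the hazard and true survival of 50 to 70%, the curve is about 1 to 3 points too high in the second case and about 1 to 1.5 points too low in the third. The sign is not fixed in advance.

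**3. Comparison of arms with no true effect.** Inputs are assumed, except for 30 per arm: true one-year survival 50% in both arms, 40% of patients frail with 3 times the hazard, dropout early (within about 8 weeks in the all-frail case), log-rank test at 5% (the protocol names no survival test).

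| Dropout A / B | Frail 3 times as likely to leave | All dropouts frail (extreme) |
|---|---|---|
| 20% / 20% | about 52% in both; difference 0 | about 55% in both; difference 0 |
| 30% / 10% | 53.1% vs 51.2%; 1.9 points; type I error 4.9% | 58.5% vs 52.1%; 6.4 points; type I error 6.8 to 7.2% |
| 35% / 10% | 53.6% vs 50.7%; 2.9 points; type I error 5.4% | 60.7% vs 52.2%; 8.5 points; type I error 7.6 to 8.5% |

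Where two error rates are shown, they come from separate runs of 3,000 and 4,000 trials. The figures move somewhat with simulation noise and the assumed timing of dropout. The last column is extreme: 30% dropout drawn only from the frail removes 0.30 / 0.40 = 75% of them, and 35% removes 0.35 / 0.40 = 87.5%. If the same patients are followed to one year whatever their dropout status, type I error stays at about 5% (4.4 to 5.4%).

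**4. Bounds without a model of who leaves.** Assume 12 dropouts among 60, 6 per arm, and 50% survival among the 24 others in each arm, so 12 known alive per arm.
- All A dropouts alive, all B dropouts dead: (12 + 6)/30 − 12/30 = 0.60 − 0.40 = +0.20.
- The reverse: 12/30 − (12 + 6)/30 = −0.20.

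If those outcomes stay unknown, the survival difference can lie anywhere from −20 to +20 points. Tracing vital status narrows this interval directly.

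**The case against.** The strongest reply is that the sentence may be harmless. If dropout means withdrawn consent or true loss to follow-up, censoring at last contact is the standard rule and matches the fix. Analysis sets and sensitivity analyses often sit in a SAP, which is not at hand. This stands in part. But the protocol states the rule affirmatively and without that limit, so staff could apply it to a patient who has merely stopped attending and is still traceable.

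Three stronger readings are tempting and are not supported.

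- *Only completers are analysed.* A reader might infer this from "The study needs 48 inclusions that remain in the study until the end". That sentence explains an extension of recruitment and matches 48 / 0.80 = 60; it defines no analysis set. Censored patients still contribute their time at risk. The two approaches also give different answers: in the 0.528 scenario above, a completers-only estimate is 0.483.
- *Sicker patients leave, mostly from one arm, so survival is biased.* No passage gives the reasons for dropout or its split by arm. The exclusion criteria remove patients with life expectancy under 3 months and those unlikely to comply. Since 2017 the intervention has lasted for the radiotherapy period, typically 5-7 weeks. Coaching might retain group A patients while controls leave, which would push the bias the other way.
- *Patients should be followed beyond one year.* The 2017 amendment shortened follow-up deliberately and gave a reason. Longer follow-up is a different design choice and is not needed to cure the censoring rule.

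**Conclusion.** The point holds as a risk created by the wording. The protocol censors dropouts on a primary mortality outcome without separating stopping the regimen or visits from loss of vital status. In an open-label trial in advanced cancer with dropout described as too high, that censoring may be informative.

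Its size cannot be fixed from the document. Under the assumed inputs the false difference between arms ranges from zero (dropout unrelated to prognosis, or the same pattern in both arms), through about 2 to 3 points with type I error near 5%, to about 6 to 8 points with type I error of roughly 7 to 8.5%. The last case needs every dropout to be frail and a 30 to 35% versus 10% split, neither of which the protocol reports. The direction could also reverse. The case for change rests on a cheap rule that removes most of the uncertainty, not on proof that bias has occurred.

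**What to change.** Replace the sentence under Replacement of subjects with:

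'All randomised patients are analysed in the arm assigned. Stopping the nutrition regimen or missing visits is not a censoring event. Vital status is obtained from existing records for every patient to one year after inclusion, where consent allows. A patient is censored only at one year or, if vital status cannot be traced, at the date last known alive.'

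Add a sensitivity analysis for patients who cannot be traced, for example bounds of the kind shown in step 4 of the working, and report dropout by arm and reason.

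The cost is a change of wording, one check of existing records, and a check of consent for patients who withdrew. The effect estimate will include patients who did not adhere, so it may look smaller. The recruitment target and the one-year follow-up are unchanged.

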Study design

randomized controlled double-blind parallel-group multi-centre study

Medication/device *If applicable*

Not applicable (enteral and parenteral nutrition, commercially available)

The subjects

Number of subjects

- Colorectal cancer (CRC) st. III - IV (TNM system) with cachexia
- Non-small cell lung cancer (NSCLC) st. III - IV (TNM system) with cachexia

120 subjects in each group, 60 controls and 60 Nutrition Therapy patients, based on statistical power. 20% extra patients were added to this number to account for dropouts.

Investigational group (Group A)

At the time of diagnosis, patients will immediately be screened and started with Nutrition Therapy if assigned to group A. This regimen will stay in place for 3 months, after which a switch will be made towards normal dietary counselling. Nutrition Therapy can be given orally, parenterally or via tube feeding, depending on the patient's status and aims at matching caloric Intake with Resting Energy Expenditure. Moreover, a switch between these modalities is possible during these 3 months. Afterwards, standard dietary counselling will be given during the remainder of the study. Follow-up will last 1 year. If one year after the last enrolment the study shows a large difference with the control group, the study will be stopped for ethical reasons.

Reference group (Group B)

At the time of diagnosis, patients will immediately be screened and started with standard dietary counselling for 2 years if assigned to group B. Dietary intervention can be orally, parenterally or via tube feeding, depending on the patient's status. Moreover, a switch between these modalities is possible during these 3 months. Follow-up will last 1 year. If one year after the last enrolment the study shows a large difference with the control group, the study will be stopped for ethical reasons.

Both Groups:

Oncological treatment will be performed at the discretion of the participating specialists, following the ESMO guidelines. Although an open label study, the oncologic treatment will not be related to the dietary regimens.

Inclusion is to take place in a period of one year. The duration of the study for each subject from randomisation to end of treatment is three months and a follow up period of nine months, for a total of one year per patient. Afterwards, analysis will take place.

Power calculation:

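### Six tumour sites in a 60-patient trial, with no site factor stated in the allocation or the analysis: a cheap gain in precision and credibility is left unused

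*Protocol*

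**What the plan says.** **Allocation.** The section Randomisation/blinding contains one sentence: "Computerized randomization, validated for clinical trials, are used". None of the three amendments revises it.

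**Size before amendment.** Number of subjects gives, for each of colorectal and non-small cell lung cancer, "120 subjects in each group, 60 controls and 60 Nutrition Therapy patients, based on statistical power". The Power calculation gives "96 patients per cancer group (48 controls and 48 nutrition therapy), supplemented with 20% per group to take dropouts into account".

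**Size after amendment.** The amendment of 12/06/2017 reduces the need to 48 patients, or 60 with dropouts: "This means 30 controls and 30 patients in the intervention group". The amendment of 05/02/2019 closes inclusion at 60 patients, dropouts counted, so 60 is the whole trial.

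**Sites.** The June 2017 amendment describes its starting point as colorectal, lung and pancreatic cancer and changes entry to "Inclusion of patients with lung, gastric, oesophageal, head and neck and pancreatic cancer". The amendment of 19/09/2017 adds "Colorectal cancer patients are still to be included". That makes six sites.

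**Analysis.** Statistical analysis names two-sided paired t-tests and nothing else. The June 2017 amendment keeps the subsets: "Analysis of the data will remain: in whole, per cancer and per sex". It adds that the last two need 60 patients in each group.

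**The concern.** Weight stabilisation, morbidity and mortality are the primary outcomes, and the protocol treats tumour site as related to them. The background to the June 2017 amendment says losses above 10% of initial weight occur especially in head and neck, oesophageal and gastric cancer. The Introduction counts pancreatic and lung cancer among the deadliest.

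With six such sites in 60 patients and only the overall arm sizes fixed, the arms can easily differ in tumour mix by chance. If neither the allocation nor the analysis uses site, the comparison carries noise that a known baseline factor could remove. A positive result would also be open to the reply that one arm simply had the more favourable tumours. That reply matters for a small trial meant to validate a 20-patient pilot.

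**Working it through.** **1. The plan's own sizes.** The protocol says "20% extra patients were added to this number to account for dropouts". Dividing by 1 − 0.20:
- 96 / 0.80 = 120 per cancer, or 60:60
- 48 / 0.80 = 60 overall, or 30:30

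Both stated figures are reproduced. The base sizes 96 and 48 cannot be checked, because alpha, power, effect and SD are not given. Nothing below depends on them.

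**2. How often site mix is uneven.** The documents give no site shares. Assume 10 patients at each of six sites and an unstratified 30:30 allocation.
- One given site: the number allocated to intervention is hypergeometric (60 patients, 30 allocated, 10 at the site). P(7:3 or worse) = 0.299.
- No site at 7:3 or worse means every site has 4, 5 or 6 in the intervention arm, with total 30. With C(10,4) = C(10,6) = 210 and C(10,5) = 252, the number of such allocations is the sum over k = 0 to 3 of [6!/(k! k! (6−2k)!)] × 210^(2k) × 252^(6−2k) = 1.842 × 10^16. Dividing by C(60,30) = 1.183 × 10^17 gives 0.156.
- P(at least one site 7:3 or worse) = 1 − 0.156 = 0.844. A simulation of 40,000 allocations gave 0.846.
- P(at least one site 8:2 or worse) = 0.37, by the same method.
- With uneven shares of 20, 14, 10, 8, 5 and 3 (assumed), P(some site differs by 4 or more patients between arms) = 0.77.

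**3. What this does to the mortality comparison.** Site mortality is also an assumption. Take one-year rates of 20, 30, 40, 45, 50 and 70%, with mean 42.5%.
- Squared deviations from the mean sum to 0.14875. Over 60 patients, S² = 10 × 0.14875 / 59 = 0.02521.
- Variance of the arm difference due to site mix = S² × (1/30 + 1/30) = 0.02521 / 15 = 0.00168. SD = 4.1 points.
- Ordinary variance of the arm difference = 2 × 0.425 × 0.575 / 30 = 0.01629. SD = 12.8 points.
- Share due to site mix = 0.00168 / 0.01629 = 10%.
- SD with site mix removed = √(0.01629 − 0.00168) = 12.1 points, about 5% lower.

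Range over other assumed rates, by the same formulas:

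| Assumed site mortality | SD from site mix | SD of arm difference, with and without site mix |
|---|---|---|
| 30 to 55%, even steps | 2.2 points | 12.8 and 12.6 points |
| 20 to 70%, as above | 4.1 points | 12.8 and 12.1 points |
| 15, 25, 35, 55, 65, 75% | 5.6 points | 12.8 and 11.5 points |

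No figure is possible for weight, since the documents give no SD by site.

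**4. What site-balanced allocation would do.** For the six sites of 10, with rates evenly spaced from 20 to 70%, simulated permuted blocks of 4 within site cut the SD from site mix from 4.5 to 1.6 points. The price is drift in the overall arm sizes: the 95th percentile of the difference is about 6 patients, and the largest seen was 12.

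**5. The per-cancer comparison.** It is said to need 60 patients in each group, and the whole trial has 60. A perfect 5:5 split in a site of 10 would not change that.

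**The case against.** A reader might infer that allocation was first balanced within tumour and that the amendment removed this. The documents do not support it. The 60:60 and 48:48 figures stand under Number of subjects and Power calculation; they are size targets. The allocation sentence names no strata in the base protocol either, so the amendments made an existing gap more important and did not create it. Nor did one amendment take the trial from two sites to six. The body has two, the June 2017 amendment describes three becoming five, and colorectal returns only in September 2017.

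Other objections also carry weight:
- Simple randomisation is valid. Chance imbalance under it brings neither bias nor type I error inflation.
- The text does not say that allocation is unstratified; it is silent. The randomisation system may hold site strata, and a statistical analysis plan that is not shown may adjust for site.
- The gain for mortality is small, about 5% of the SD under the main assumption.
- Changing the allocation helps only patients not yet randomised.

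These points limit the size of the concern but do not remove it. The protocol does state an analysis, and that analysis has no site term. Site is recorded at baseline for every patient, and the protocol itself links it to weight loss.

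**Conclusion.** The point holds as a cheap improvement. Six sites share 60 patients at 30:30 overall, and neither the allocation sentence nor the stated test uses site. Uneven site mix is then likely: about 84% for at least one site at 7:3 or worse, assuming equal sites of 10 and unstratified allocation. The consequence is some lost precision and credibility. For mortality, the SD of the arm difference would fall from 12.8 to between 12.6 and 11.5 points over the assumed ranges, and to 12.1 under the main one. It would be too strong to say that the comparison is invalid or that a positive result would be an artefact of case mix. The per-cancer comparison is uninformative for lack of patients, whatever the allocation. Severity: worth considering.

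**What to change.** Amend Statistical analysis and Randomisation/blinding along these lines:

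*The arms are compared on weight with a between-arm model that includes tumour-site group (head and neck; oesophageal and gastric; pancreatic; lung; colorectal) as a factor. The survival comparison is adjusted for the same groups, merged further where a group is too small. Patients still to be randomised are allocated by minimisation on these groups. Results per cancer are descriptive.*

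The adjustment applies to all patients, including those already allocated, and so does most of the work. The between-arm model is needed in any case, because a paired test does not compare two parallel arms.

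**Cost.** Five groups use four degrees of freedom in the weight model, and survival strata may be thin, hence the rule to merge further. Minimisation is preferred to blocks within site because incomplete blocks in small sites can pull the totals away from 30:30. It needs a change to the randomisation system, and is worth making only if enough patients remain to be randomised.

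### The paired t-test stated for the primary weight outcome does not compare the two randomised arms or adjust for starting weight; an analysis of covariance would do both, though the precision gain is probably small

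*Protocol*

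**What the plan says.** The section on statistical analysis reads, in full, "2-tailed, paired t-tests will be used for statistical analysis". The only other method named anywhere is Kaplan-Meier, under Replacement of subjects, where it concerns the censoring of dropouts and so does not apply to weight.

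The outcomes are given as "Primary: weight stabilisation, morbidity and mortality", with no scale, definition or time point for stabilisation. Body weight occurs three times in the list under Analysis of the samples, the last time as "Body weight, mortality, morbidity".

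Under Study design the trial is a "randomized controlled double-blind parallel-group multi-centre study". Only the parallel-group element matters here.

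The amendment of 12/06/2017 says that "only 48 patients will be needed instead of 96" and that "With correction for dropouts, this will become 60 patients instead of 120", split 30 and 30. The amendment of 05/02/2019 repeats the target: "The study needs 48 inclusions that remain in the study until the end". The background to the 2017 amendment describes radiotherapy patients as "losing > 10% of their initial body weight (at the start of their therapy"), so starting weight is the reference it uses for loss.

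**The concern.** The question the trial asks about weight is whether patients given nutrition therapy hold their weight better than controls. A paired t-test answers a different question: whether weight changed within a set of patients. In a parallel-group trial that is not a treatment comparison. If it were run in each arm and the results set side by side, one arm could be significant and the other not when nothing differs between them.

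Simply changing paired to independent would give a between-arm test but would still not model starting weight. With small arms, several tumour sites and both sexes, the arms can differ in starting weight by chance. A test on final weight carries that imbalance in proportion to rho. A test on change carries part of it with the opposite sign, because subtraction fixes the slope at 1.

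This is not a silence that an analysis plan may fill. The protocol names the test, and an analysis plan that followed it would contain no between-arm comparison of weight.

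**Working it through.** **Inputs from the protocol.** 48 completers; 30:30 allocation; so 48/2 = 24 per arm.

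**The plan's own figure.** The enrolment figure reproduces as 48/(1 − 0.20) = 60, and the superseded one as 96/(1 − 0.20) = 120. The 48 itself cannot be reproduced. The protocol refers to the pilot trial but gives no alpha, power, effect or standard deviation, and does not say that the number was sized on weight.

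**Assumptions.** Two-sided alpha 0.05; 80% power for an unadjusted between-arm t-test; equal variance of weight at start and end; rho varied. At 24 per arm the detectable difference is then 0.81 SD by the normal formula, (1.96 + 0.84) × √(2/24), or 0.83 SD with the t distribution on 46 degrees of freedom.

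**Step 1: what within-arm paired tests would show.** Suppose both arms have the same true change and each paired test has power p. The chance that exactly one arm is significant is 2p(1 − p): 0.42 at p = 0.3, 0.50 at p = 0.5, 0.32 at p = 0.8. So a pair of within-arm results is no evidence about the difference between arms. If pairing meant matching patients across arms, no matching is described; 24 unrelated pairs would leave 23 degrees of freedom instead of 46, and power would fall from 80% to 78%.

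**Step 2: chance imbalance.** The difference in mean starting weight has standard error √(2/24) = 0.29 SD. A difference above 0.3 SD in either direction (0.3/0.29 = 1.04 standard errors) occurs in about 30% of trials. A change score carries a share (1 − rho) of it: 50% at rho 0.5, 10% at 0.9, 5% at 0.95. Covariance adjustment removes it, given a linear relation.

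**Step 3: precision.** With the SD of final weight set to 1, the variances are:
- final weight alone: 1
- change: 2(1 − rho)
- analysis of covariance: 1 − rho²

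The variance ratio of covariance analysis to change is therefore (1 + rho)/2, and to final weight 1 − rho². The effect was set to give the unadjusted test 80% power, and power was recomputed by noncentral t on 45 degrees of freedom:

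| rho | Variance ratio to change | Power, if change test has 80% | Variance ratio to final weight | Power, if final-weight test has 80% |
|---|---|---|---|---|
| 0.3 | 0.65 | 93.5% | 0.91 | 83.5% |
| 0.5 | 0.75 | 89.9% | 0.75 | 89.9% |
| 0.7 | 0.85 | 85.9% | 0.51 | 97.5% |
| 0.9 | 0.95 | 81.9% | 0.19 | >99.9% |
| 0.95 | 0.975 | 80.9% | 0.10 | >99.9% |

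Estimating the slope inflates the variance by about 1 + 1/44. By the normal approximation, the power in the change comparison then becomes 89.2%, 85.2%, 81.1% and 80.1% at rho 0.5, 0.7, 0.9 and 0.95, and 79.5% at 0.98. The gain is roughly nil from 0.95 upwards.

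**Step 4: which rho is credible.** The SD of change equals the SD of weight times √(2(1 − rho)). With an assumed between-patient SD of 15 kg, this is 15 kg at rho 0.5, 6.7 kg at 0.9 and 4.7 kg at 0.95. The 2017 amendment puts radiotherapy at typically 5–7 weeks. Changes that vary as much as weight varies between patients are hard to believe over that time, so 0.9 or more is the likelier range.

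**The case against.** A covariate in the weight model is commonly left to an analysis plan, and the one for this trial is not at hand, so its absence alone would be a weak point. That stands. It does not protect the sentence in the protocol, which fixes a test unsuited to two independent arms.

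A second objection is that a paired test already uses starting weight by subtraction. That is also right, and it limits the precision argument: against a change score the extra gain is about 0–2 points at rho 0.9 or more.

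Two stronger readings are tempting. From the right-hand column of the table a reader might infer that the trial throws away most of its precision. That needs a test on final weight alone. No section states one, and both stabilisation and pairing point to change. A reader might also infer that the 2017 amendment defines the trial's weight endpoint as loss from starting weight. It does not: the text is background on patients whom the radiotherapy service sees.

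Finally, the visit labels cannot be read in the text at hand. That every patient has a starting weight is inferred from the repeated weight entries and from the outcome itself, since stabilisation cannot be judged without one.

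**Conclusion.** The point holds in a limited form. The one test stated for a primary outcome gives no comparison of the randomised arms and no adjustment for starting weight. The main reason to change it is validity: a between-arm estimate with a confidence interval, free of chance baseline imbalance at 24 per arm.

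Greater precision is a secondary reason and probably a small one: from 80% to about 82% at rho 0.9 and 80–81% at 0.95, with nothing left at 0.95 and above once slope estimation is counted. It would reach about 86% at rho 0.7 and 90% at 0.5. These figures rest on an assumed alpha, an assumed 80% power, equal variances and an unreported rho, so none can be stated as this trial's actual loss.

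**What to change.** For the weight outcome, replace the t-test sentence with:

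> Body weight at the end of the intervention will be compared between the randomised arms by analysis of covariance, with arm as factor and body weight at the start of therapy as covariate; the adjusted mean difference with its 95% confidence interval is the primary result for weight.

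This wording also supplies a scale and a time point, which the protocol lacks, so the sponsor should confirm that both match what is meant by stabilisation and that the two weights are on the visit schedule. If stabilisation is meant as a yes/no or percentage outcome, the sentence needs adapting, still as a between-arm analysis adjusted for starting weight.

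The cost is one sentence, one degree of freedom and the slope-estimation loss of up to about one percentage point of power. If both weights are already collected, no new data, visits or patients are needed.
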